8.7.2. NLF-SRS Response Rate – Blinded Independent Photographic Reviewer

NLF-SRS response rate based on independent blinded photographic reviewers assessments of photograph (NLF severity) at Week 12, 36, 48 and the post repeat-treatment hold follow-up visit (Visit 7c) compared to Baseline using the NLF-SRS. This endpoint will be analyzed descriptively presenting the response rate and one-sided 95% CIs using McNemar type test given in [section 8.2.1](#), and the individual independent ratings will also be analyzed using pairwise Kappa statistics to assess inter-rater consistency among the three independent blinded photographic reviewers.

The Kappa test for consistency in SAS statements could refer:

```
Proc freq data=xxxxxxxxx;  
  tables Reviewer1 * (Reviewer2 Reviewer3) / agree;  
  tables Reviewer2 * Reviewer3 / agree;  
  test kappa;  
Run;
```

8.7.3. NLF-SRS Response Rate – Treating Investigator

NLF-SRS response rate based on treating investigator live assessments of NLF severity at Week 12, 36, 48 and the post repeat-treatment hold follow-up visit (Visit 7c) compared to Baseline using the NLF-SRS. This endpoint will be analyzed descriptively presenting the response rate and one-sided 95% CIs using McNemar type test given in [section 8.2.1](#).

8.7.4. GAIS Response Rate - Blinded Independent Evaluating Investigator

Aesthetic response rate based on blinded independent evaluating investigator assessment at Week 12, 36, 48 and the post repeat-treatment hold follow-up visit (Visit 7c) relative to Baseline using the GAIS. This endpoint will be analyzed descriptively presenting the response rate and one-sided 95% CIs using McNemar type test given in [section 8.2.1](#).

8.7.5. GAIS Response Rate - Subject Assessment

Aesthetic response rate based on subject assessment at Week 12, 36, 48 and the post repeat-treatment hold follow-up visit (Visit 7c) relative to Baseline using the GAIS. This endpoint will be analyzed descriptively presenting the response rate and one-sided 95% CIs using McNemar type test given in [section 8.2.1](#).

8.7.6. FACE-Q Subject Satisfaction with Outcome

FACE-Q subject satisfaction with aesthetic outcome at Weeks 12, 24, 36, 48 and the post repeat-treatment hold follow-up visit (Visit 7c) relative to Baseline. For tabulation, Week 36, Week 48 and Visit 7c data will be combined into one additional virtual post repeat-treatment visit. This endpoint will be analyzed using Wilcoxon signed-rank test.

SAS code for Wilcoxon signed-rank test could refer:

This document is confidential.

```
proc univariate data=xxxxxx;  
  var diff;  
run;
```

8.7.7. FACE-Q Subject Appearance Appraisal of NLF

FACE-Q subject appearance appraisal of nasolabial folds at Weeks 12, 24, 36, 48 and the post repeat-treatment hold follow-up visit (Visit 7c) relative to Baseline. For tabulation, Week 36, Week 48 and Visit 7c data will be combined into one additional virtual post repeat-treatment visit. This endpoint will be analyzed using Wilcoxon signed-rank test.

8.7.8. Subjects Perception of Pain

Subjects' perception of pain will be compared between the treatment groups after initial treatment with Princess® FILLER Lidocaine and with Juvéderm® Ultra XC and after repeat treatment with Princess® FILLER Lidocaine, using a scale adapted from the 11-point Numeric Pain Rating Scale (NPRS), where 0 indicates 'no pain' and 10 indicates 'worst possible pain'. This endpoint will be analyzed using a longitudinal mixed model for repeated measures (MMRM) with fixed effects for treatment, timepoint, treatment-by-timepoint interaction, and baseline pain score as covariate. Subject will be the random effect. The unstructured covariance matrix for repeated observations within subjects will be used.

The least square (LS) means and standard error of each treatment, LS means differences including standard error, 95% confident interval (CI) and 2-sided p-values for the treatment difference for the pain scores at Weeks 36, 48 and the post repeat-treatment hold follow-up visit (Visit 7c) and for each scheduled time point will be presented in the tables.

SAS code for MMRM model could refer:

```
ods output lsmeans=lsmeans diffs=diffs tests3=test;  
proc mixed data=xxxxxxx method=REML;  
  class subject treatment timepoint;  
  model score=base treatment timepoint treatment*timepoint/ddfm=kr;  
  repeated timepoint/sub=subject type=un;  
  lsmean treatment*timepoint/pdiff cl;  
run;
```

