10.4 Subject's Evaluation of Pain

The subject's perception of pain will be evaluated for treatments with Princess® FILLER Lidocaine and Juvéderm® Ultra XC.

This evaluation will be assessed using a scale adapted from the 11-point NPRS, where "0" indicates "no pain" and "10" indicates "the worst pain imaginable".

The evaluation of subject's pain will be done starting 15 min (+/- 3 min) after last injection and at 15 min-intervals (+/- 3 min) for 60 min (+/- 3 min) post-treatment (initial and repeat-treatments) using the adapted NPRS.

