10.11.2 Baseline (Visit 2)

The following procedures and/or assessments will be performed at Baseline (Visit 2), Day 0:

- Body weight measurement
- Visual examinations (including Snellen visual acuity, confrontational visual fields and ocular motility) prior to- and 30 min after the treatment (see Section 10.8)
- Evaluation of eligibility criterion based on visual examinations
- Urine pregnancy test in women of childbearing potential only, including those who are postmenopausal for less than twelve months (prior to treatment)
- Randomization (prior to treatment)
- Treatment (initial treatment)
- Live assessment of nasolabial fold severity by treating investigator using NLF-SRS (prior to treatment)
- Live assessment of nasolabial fold severity by the independent blinded evaluating investigator using NLF-SRS (prior to treatment)
- Photography (prior to treatment)
- Evaluation of pain assessment by the subject using the adapted NPRS
- FACE-Q subject appearance appraisal questionnaire ("appraisal of nasolabial folds") (prior to treatment)
- Dispense of subject diary
- Assessment of injection volume
- AEs (prior to treatment)
- Concomitant medications/procedures (prior to treatment)

10.11.3 Phone Contact after Visit 2

The following assessments will be performed at Day 3 (± 24 hours) after Visit 2:

- AEs including if subjects are experiencing or have experienced any signs/symptoms of vision changes or stroke since the injection
- Concomitant medications/procedures

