2.9. Administration of Study Medication

On Day 0 (Visit 2), the Princess® FILLER Lidocaine will be injected to one NLF and the control Juvéderm® Ultra XC to the contralateral NLF of each subject, according to the randomization scheme; the left NLF will be treated first and the right NLF thereafter.

The decision to perform touch-up treatment is in the responsibility of the treating investigator and aim to obtain optimal aesthetic result, if not already achieved with the initial treatment.

A repeat-treatment will be performed with Princess® FILLER Lidocaine on both NLFs.

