- i Evaluation of aesthetic improvement using the Global Aesthetic Improvement Scale (GAIS)
- j Subject diary to be collected and reviewed two and four weeks after initial-touch-up treatment, and four weeks after repeat-treatment
- k Starting 15 min after last injection and at 15 min-intervals for 60 min post-treatment using the adapted NPRS.

This document is confidential.

3. Outcome Measures

The outcome measures will be separately evaluated for the left and right side of the face.

Responder is defined as having at least one grade improvement over Baseline, on the 5-point NLF-SRS.

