3.3. Additional Effectiveness Outcome Measures

1. The percentage of responders based on the independent blinded evaluating investigator live assessment at Week 12, 36, 48 and Visit 7c after initial treatment and compared to Juvéderm® Ultra XC
2. The percentage of responders based on the independent blinded photographic reviewers assessments at Week 12, 36, 48 and Visit 7c after initial treatment, compared to Juvéderm® Ultra XC and based on photographs
3. The percentage of responders based on the treating investigator live assessment at Week 12, 36, 48 and Visit 7c after initial treatment and compared to Juvéderm® Ultra XC
4. The percentage of subjects with an improvement over Baseline (subjects who have been rated as “very much improved” or “much improved” or “improved”), based on the independent blinded evaluating investigator assessment at Week 12, 36, 48 and Visit 7c after initial treatment and using the 5-point GAIS
5. The percentage of subjects with an improvement over Baseline (subjects who have been rated as “very much improved” or “much improved” or “improved”), based on subject assessment at Week 12, 36, 48 and Visit 7c after initial treatment and using the 5-point GAIS
6. The extent of subject satisfaction with outcome of the treatment, as assessed by the Face-Q questionnaire “Satisfaction with Outcome” at Week 12, 24, 36, 48 and Visit 7c after initial treatment
7. Subject appearance appraisal after treatment as assessed by the Face-Q questionnaire “Appraisal of Nasolabial Folds” at Week 12, 24, 36, 48 and Visit 7c after initial treatment, relative to Baseline
8. Subject’s perception of pain after initial with Princess® FILLER Lidocaine and with Juvéderm® Ultra XC and after repeat-treatment with Princess® FILLER Lidocaine, using a scale adapted from the 11-point Numeric Pain Rating Scale (NPRS), where 0 is no pain and 10 is the worst pain imaginable.

This document is confidential.

9. Time from initial to repeat-treatment for each treatment group will be assessed by tabulating the following rates:
 - repeat-treatment at Week 36
 - repeat-treatment at Week 48
 - repeat-treatment at Visit 7c
 - no repeat-treatment
10. Recording of injection volume required to achieve optimal correction for Princess® FILLER Lidocaine and Juvéderm® Ultra XC at initial and touch-up treatments and recording of injection volume required to achieve optimal correction for Princess® FILLER Lidocaine at repeat-treatments (separate assessments)

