6.2. Key Definitions

The study day is the day relative to the date of first administration of Investigational Medical Device (IMD), where Day 1 is the day of first administration of IMD.

The first dose date is defined as the first non-missing date where an administration of IMD was recorded. The last dose date is defined as the last non-missing date where an administration of IMD was recorded.

For on-treatment events (on or after first dosing day), Study Day = Event Date - date of first administration of IMD + 1; and for pre-treatment events (prior to first dosing day), Study Day = Event Date - administration of IMD.

Unless otherwise specified, baseline is the last non-missing observation before the administration of IMD, which is expected to be Day 1, or Screening if the Day 1 data are not available.

This document is confidential.

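### The SAP 8.7.8 pain model cannot be run as written: its baseline covariate is never collected, the repeat-visit filler contrast does not exist, and the score analysed is unclear

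*SAP*

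**What the plan says.** SAP 8.7.8 specifies a longitudinal mixed model for the 11-point pain score. It has fixed effects for treatment, timepoint, "treatment-by-timepoint interaction, and baseline pain score as covariate", a random subject effect and an unstructured within-subject covariance. The sample code carries the covariate as `base`. The section asks for LS-mean differences, confidence intervals and "2-sided p-values for the treatment difference for the pain scores at Weeks 36, 48", and also at Visit 7c and each scheduled timepoint.

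Other passages bear on whether this can be done:

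- **Baseline.** SAP 6.2: "Unless otherwise specified, baseline is the last non-missing observation before the administration of IMD". Section 8.7.8 gives no other definition.
- **Timing of ratings.** Protocol 10.4: "The evaluation of subject's pain will be done starting 15 min (+/- 3 min) after last injection". SAP 8.1.5 repeats this, and footnote k of SAP Table 1 reads "Starting 15 min after last injection and at 15 min-intervals for 60 min post-treatment using the adapted NPRS".
- **Visit 2 procedures.** Protocol 10.11.2 lists "Evaluation of pain assessment by the subject using the adapted NPRS" without the prior-to-treatment tag that several other items carry.
- **Device at repeat-treatment.** SAP 2.9: "A repeat-treatment will be performed with Princess® FILLER Lidocaine on both NLFs". Outcome measure 8 in SAP 3.3 names both fillers after initial treatment, but only Princess later: "after repeat-treatment with Princess® FILLER Lidocaine, using a scale adapted from the 11-point Numeric Pain Rating Scale (NPRS".
- **Score used.** SAP 8.1.5 collects left, right and overall scores, sends the overall score to the summary and lists all three. SAP 8 calls for presentation by filler and for the within-subject difference between the two treated sides.

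**The concern.** Four parts of the specification do not fit the data that the trial collects: the covariate, the repeat-visit contrast, the score and the covariance. Someone following the SAP literally gets an empty model. Someone repairing it at the programming stage must choose a substitute baseline, a score, a coding of treatment and a covariance structure, with no prespecified rule for any of them.

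Protocol 14.2 planned only descriptive statistics for these outcomes. SAP 11 adds confidence intervals and/or p-values for all additional objectives, so inferential pain output was a deliberate addition. At repeat-treatment, a p-value labelled as a treatment difference could be read as a device comparison that was never made.

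**Working it through.** The plan gives no figure for this analysis, so there is none to reproduce. The check sets the model against the data schedule.

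**1. Baseline covariate.** Inputs: 270 randomized subjects (SAP 2.6), ratings at 15, 30, 45 and 60 minutes (SAP 8.1.5), two folds.

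- Side-score records after initial treatment: 270 × 4 × 2 = 2,160.
- Overall-score records: 270 × 4 = 1,080.
- Scheduled ratings before the first injection: 0. Both schedules show pain at Baseline and at repeat-treatment visits only. In SAP Table 1 the Baseline entries for photography and FACE-Q appraisal carry the prior-to-treatment footnote; the pain entry does not.

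A record without the covariate drops out, so 0 of 2,160 (or 0 of 1,080) remain. Taking the 15-minute score as baseline would contradict SAP 6.2 and make an outcome its own covariate.

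**2. Contrast at repeat-treatment.** A rank test of estimability was run on a toy layout: 270 subjects, two folds, four timepoints at the initial visit and four at one repeat visit.

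| Treatment coded as | Initial visit, 4 timepoints | Repeat visit, 4 timepoints |
|---|---|---|
| Filler injected | estimable | not estimable (Juvéderm cells empty) |
| Filler originally assigned to that side | estimable | estimable, but compares Princess after Princess with Princess after Juvéderm |

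Neither coding gives a contrast between injected devices at Weeks 36, 48 or Visit 7c.

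**3. Which score.** The overall score is one value per subject and timepoint. Assigned to both fillers, it gives a difference of exactly 0 for every subject; assigned to one, it is not that filler's pain. A filler comparison therefore needs side scores, which SAP 8.1.5 only lists. SAP 8.7.8 does not name its score.

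**4. Covariance, if side scores are used.** The sample code indexes repeated observations by timepoint within subject, with no fold or treatment level. Each subject has 8 rows (2 folds × 4 times) mapped to 4 levels.

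- Coded covariance: R = Z U Z′, with U a 4×4 positive-definite matrix and Z of size 8×4. R is 8×8 with rank 4 and determinant 0.
- The random subject intercept named in the text but absent from the code adds σ²J. The vector of eight ones equals Z times the vector of four ones, so R + σ²J = Z(U + σ²J₄)Z′, still rank 4.
- With treatment-by-timepoint as the repeated effect, the matrix is an unstructured 8×8 of rank 8, with 8 × 9 / 2 = 36 parameters.

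The Gaussian likelihood needs the inverse and the log-determinant of this matrix. It is undefined in the first two cases and defined in the third.

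**The case against.** The strongest reply is that much of this is loose drafting around an exploratory outcome.

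- **A fallback exists.** SAP 8 already prespecifies descriptive statistics, with a two-sided 95% confidence interval, for the difference between the two treated sides. This stands as a descriptive result. It supplies no baseline, score or covariance for the mixed model, and SAP 8.1.5 still directs the summary to the overall score.
- **Allocation is protected.** It is not to be revealed before the database is cleaned and closed, so late choices need not be data-driven. That is fair; the complaint is the missing rule, not suspected selection.
- **The code is only an example.** SAP 8.7.8 presents it as something to refer to, and the prose on covariance is compatible with a treatment-by-timepoint structure. This reduces the covariance point to a faulty sample line. The baseline covariate, however, is in the prose too.
- **The repeat-visit contrast can be computed.** SAP 4.2 analyses the FAS by randomized treatment, and under that label the contrast is estimable. True, but it then measures earlier filler, which the SAP never states as its aim.
- **Summary and model may use different scores.** Descriptive tables could use the overall score while the model uses side scores. That would ease the conflict for the model, but it is not stated, and the tables would still conflict with SAP 8. The score and covariance problems also belong to alternative readings and should not be added together.

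The missing baseline has no answer in the documents.

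**Conclusion.** The concern holds. The missing pre-injection score alone leaves the model with no usable records. This rests on the SAP 6.2 definition applying, since 8.7.8 sets no exception, and on the schedules being complete for pain ratings. The repeat-visit contrast is either not estimable or not a comparison of the injected devices. The score is not identified, and with side scores the sample covariance is singular whether or not a random intercept is added.

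The consequence is limited. Pain is an additional outcome, exploratory under the protocol synopsis and outside the hierarchical procedure. No primary, key secondary or safety conclusion depends on it. The specification should be corrected, but it does not threaten the trial's main result.

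**What to change.** Reconcile SAP 8, 8.1.5 and 8.7.8:

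1. In 8.1.5, state that left and right scores are summarised and analysed by filler, and that the overall score is listed or shown separately.
2. In 8.7.8, delete the baseline pain covariate from the text and `base` from the code.
3. For initial treatment, compare Princess with Juvéderm within subject at 15, 30, 45 and 60 minutes. Either model the paired Princess minus Juvéderm difference with timepoint as the repeated effect, or keep both scores and use `repeated treatment*timepoint / sub=subject type=un`. Name one of these in the SAP, and make the text on the subject effect match the code.
4. After repeat-treatment, describe Princess pain by session and timepoint, with no treatment difference or p-value.

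The cost is SAP wording and program changes only, because side-specific scores are already collected.

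The documents give no pain SD or left/right correlation, so the precision of the paired difference can be shown only under assumptions. With SE = SD × √(2(1 − ρ)/270):

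| Assumed SD | Assumed ρ | SE (points) |
|---|---|---|
| 1 | 0.8 | 0.038 |
| 2 | 0.6 | 0.109 |
| 3 | 0.3 | 0.216 |

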8.1.5. Subject's Evaluation of Pain

The subject's perception of pain will be evaluated for treatments with Princess® FILLER Lidocaine and Juvéderm® Ultra XC. This evaluation will be assessed using a scale adapted from the 11-point Numeric Pain Rating Scale (NPRS), where "0" indicates "no pain" and "10" indicates "the worst pain imaginable".

The evaluation of subject's pain will be done starting 15 min (+/- 3 min) after last injection and at 15 min-intervals (+/- 3 min) for 60 min (+/- 3 min) post-treatment (initial and repeat treatments) using the adapted NPRS. Separate assessments will be performed for the left and the right side of the face and overall. Overall assessment will be used for summary, and left, right side and overall assessments will be listed.

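### The pain model in SAP 8.7.8 cannot give the device differences it promises: side ratings make its covariance block singular, and the overall rating has no device label

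*SAP*

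**What the plan says.** SAP 8.7.8 plans a repeated-measures mixed model for the 11-point pain score, with treatment, timepoint, their interaction and a baseline pain score. In the text, "Subject will be the random effect" and "The unstructured covariance matrix for repeated observations within subjects will be used". The promised output is LS means per treatment and LS-mean differences with standard error, 95% interval and "2-sided p-values for the treatment difference for the pain scores at Weeks 36, 48" and Visit 7c, and also at each scheduled time point.

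The sample code has "class subject treatment timepoint" in its CLASS statement and "repeated timepoint/sub=subject type=un" as its only covariance statement. It has no RANDOM statement and no variable for side.

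SAP 8.1.5 has pain rated at 15, 30, 45 and 60 minutes after the last injection. "Separate assessments will be performed for the left and the right side of the face and overall". The next sentence reads: "Overall assessment will be used for summary, and left, right side and overall assessments will be listed".

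Under SAP 2.8 each face receives one device per fold at initial treatment. Under SAP 2.9 both folds receive Princess at repeat treatment.

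**The concern.** Both devices are in every face, so a device difference in pain is a within-face contrast and needs two labelled scores per subject at each time. The coded covariance statement allows for one score per subject at each time. The rating that 8.1.5 reserves for summaries is one score per subject at each time, but it belongs to neither device. Whichever rating is used, the output listed in 8.7.8 cannot be produced by the model in 8.7.8.

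The programmer would therefore have to choose a repair, possibly after the database is closed and the assignments are known. The repairs are not interchangeable. Some keep the split-face pairing, and at least one discards it.

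**Working it through.** The documents give no sample size, standard error or power for the pain model, so there is no stated figure to reproduce.

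**Inputs.** 4 times per session and three ratings (left, right, overall) per time, from SAP 8.1.5. One device per fold at initial treatment, from SAP 2.8. The covariance statement, from SAP 8.7.8. The between-fold correlation rho of pain is not in the documents; it is assumed, and a range is shown.

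**Step 1: side ratings, code as written.** Let Sigma be any positive definite 4 x 4 unstructured matrix over the four times. Each time level occurs twice in a subject, so the 8 rows map to 4 levels through Z, two 4 x 4 identity matrices stacked. The implied block is

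V = Z Sigma Z' = [Sigma, Sigma; Sigma, Sigma].

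Its rank is that of Sigma, 4 of 8. With one example Sigma, the eigenvalues of V were 20.20, 3.23, 1.59, 0.98 and four zeros, and the log-determinant was minus infinity. The zero directions are the differences between folds at the same time: for c = (1 for Princess, -1 for Juvéderm) at one time, c'Vc = 0. The model gives zero variance to the contrast it is meant to estimate, for any Sigma.

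**Step 2: add the random subject effect only.** This adds s² times an 8 x 8 matrix of ones, which equals Z(s²J)Z' with J the 4 x 4 matrix of ones. Hence V = Z(Sigma + s²J)Z', still of rank 4.

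**Step 3: other data the SAP could be read to use.**

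| Data in the model | Rows per subject | Rank of V | Device contrast |
|---|---|---|---|
| Left and right, initial session | 8 | 4 | defined, but V singular |
| Left, right and overall stacked | 12 | 4 | V singular |
| Left and right, initial plus one repeat session | 16 | 8 | V singular |
| Overall only, initial session | 4 | 4 | none: one score reflects both devices |

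**Step 4: possible repairs.** Using subject-by-fold as the repeated subject gives rank 8 of 8, but sets the between-fold covariance to zero. Adding the random subject effect to that repair also gives rank 8 of 8, and makes the between-fold covariance equal to the subject variance (1.5 in the example), so the pairing is kept.

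**Step 5: cost of the repair without the random effect.** With common standard deviation sd and N subjects, the paired SE at one time is sqrt(2 sd²(1 - rho)/N) and the unpaired SE is sqrt(2 sd²/N). Their ratio is f = 1/sqrt(1 - rho). For illustration take sd = 2 (assumed) and N = 270 (SAP 2.6): the unpaired SE is sqrt(8/270) = 0.172. A difference that has 80% power when paired has power 1 - Phi(1.96f - 2.80) when the pairing is ignored.

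| rho (assumed) | f | Paired SE | Power, pairing ignored |
|---|---|---|---|
| 0.3 | 1.20 | 0.144 | 68% |
| 0.5 | 1.41 | 0.122 | 51% |
| 0.7 | 1.83 | 0.094 | 22% |

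**The case against.** The strongest reply is that the matrix need not be singular at all. SAP 8.1.5 designates the overall rating for summary and only lists the side ratings. With one row per time, the unstructured matrix has full rank. That is correct, and a reader who infers that the planned matrix is singular whatever data are used goes further than the documents allow. But this reading does not rescue the analysis. In a face with one device on each side, the overall score has no treatment value, so the differences in 8.7.8 do not exist.

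A second reply is that nobody has planned to discard the pairing. This also stands. A reader might infer that the pain standard errors will be too large by a big factor. Neither document proposes fold as its own subject, the text already names a random subject effect that would keep the pairing under that repair, and rho is an assumption. For positive rho the error would also be conservative, widening intervals without creating false differences. The inflation factors are a caution about one possible repair.

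Third, the code is offered as a sample, and pain is additional outcome 8, outside the testing hierarchy in SAP section 8. The protocol synopsis treats everything outside that hierarchy as exploratory. A singular likelihood should also show itself at programming. This limits the severity, but does not make the specification workable: the text alone does not say which rating is analysed or how fold enters the covariance.

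**Conclusion.** Wrong as written, low severity. On the side ratings the coded model has a within-subject block of rank 4 of 8 and no evaluable REML likelihood. On the overall rating it has no device contrast. These two results follow from the SAP's own code and rating scheme and need no assumption about the data. Only the inflation factors of 1.20 to 1.83 depend on an assumed correlation (0.3 to 0.7), and they apply only if fold becomes its own subject without a random subject effect. The primary and key secondary conclusions are untouched. The point still merits correction, because SAP section 11 commits to intervals and/or p-values for all additional objectives and pain tables are planned for both the FAS and the PPS.

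**What to change.** 1. Reconcile SAP 8.1.5 with 8.7.8. State that the left and right ratings are used for the device comparison after initial treatment, and keep the overall rating for description.

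2. Model the within-face difference, Princess minus Juvéderm, at each time: `model diff = timepoint; repeated timepoint / subject=subject type=un; lsmeans timepoint / cl;`. This follows SAP section 8, which already asks for the mean difference between a subject's two sides with a two-sided 95% interval, and 8.7.6, which tests a difference variable.

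3. Side may be added because the left fold is always injected first while ratings run from the last injection. A single side term removes only an order effect that is constant over time; side-by-timepoint would be needed otherwise. Side allocation is randomised 1:1, so either term is optional.

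4. If both folds are to stay in the model, use a fold-by-time unstructured matrix within subject, or fold as the repeated subject together with the random subject effect the text already names. Do not use fold as its own subject alone.

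5. In the same edit, settle two neighbouring items. The model takes a baseline pain score, but the schedule starts ratings 15 minutes after injection. After repeat treatment both folds carry Princess, so a difference between folds at Week 36, Week 48 or Visit 7c is not a device difference, and those sessions should be described separately.

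The cost is a few lines of SAP text and a shorter model. No new data are needed, because both side ratings are already planned for collection.
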